6.2. CORRELATIVES WITH BLOOD

Blood samples must be submitted with the submission form documenting the date of collection of the sample. Blood samples will be obtained at baseline and prior to each nivolumab infusion during radiation therapy; subsequently blood will be obtained at weeks 18, 30 52, and 104 as outlined in study calendar above. Peripheral blood mononuclear cells (PBMCs) and plasma will be isolated from collected CPTs and cryopreserved as outlined in the blood processing Appendix 3.

Specimen collection summary for correlative studies (Samples can be batched and sent in one shipment)

Specimens for Correlative Studies			
Specimens taken from patient:	Collected when:	Submitted as:	Shipped:
A paraffin-embedded tissue of the primary tumor taken before initiation of treatment	Pre-treatment	Paraffin-embedded tissue block	Block shipped ambient
Fresh frozen tissue of the primary or metastatic tumor taken before initiation of treatment (for research purposes only: OPTIONAL)	Pre-treatment	Frozen tumor in a 2 mL cryovial	Tumor sent frozen on dry ice via overnight carrier
A paraffin-embedded tissue of the primary or metastatic tumor (for research purposes only: OPTIONAL)	At the time of disease progression	Paraffin-embedded tissue block	Block shipped ambient
Fresh frozen tissue of the primary or metastatic tumor (for research purposes only: OPTIONAL)	At the time of disease progression	Frozen tumor in a 2 mL cryovial	Tumor sent frozen on dry ice via overnight carrier
PBMCs and PLASMA: 4 CPTs (8 mL each) of whole blood for	Pre-treatment and prior to each Nivolumab infusion during radiation	Frozen plasma samples containing 2 mL per aliquot in 2 mL cryovials:	Plasma sent frozen on dry ice or liquid nitrogen via overnight carrier

collection of plasma and PBMCs	therapy ; subsequently at wk 18, 30, 52 and 104.	Cryopreserved PBMCs containing 10^7 PBMCs per aliquot in 2 mL cryovials	
--------------------------------	--	---	--

Submit materials for translational research as following:

U. S. Postal Service Mailing Address:

[name] Lab

Department of Microbiology & Immunology

Emory University

[name]

[name]

Or

[name] Laboratory

Cleveland Clinic Foundation

Department of Translational Hematology Oncology Research

[name]

Lerner Res Stockroom

NE6-258 [name] Lab

[name]

For Non-urgent, Non-frozen Specimens Only

Courier Address (FedEx, UPS):

[name] Lab

Department of Microbiology & Immunology

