6.3. PROPOSED BIOMARKER EVALUATIONS

A. Despite the unprecedented success of PD-1 targeted therapies a significant number of patients still fail to respond due to mainly unknown reasons. A deeper understanding of the mechanisms underlying responsiveness to blockade of the PD-1 pathway and the identification of predictive biomarkers are thus essential to optimize current treatments and to develop novel treatment approaches in order to improve response rates. Two recent studies analyzing the CD8 T cell response in the peripheral blood of non-small lung cancer and melanoma patients undergoing PD-1 targeted therapies observed an increase in activated and proliferating PD-1+ CD8 T cells in a subset of patients which in combination with tumor burden correlated with clinical outcome (37, 38). We will therefore monitor T cell activation and proliferation in the peripheral blood by multi-parameter flow cytometry of isolated PBMCs including but not limited to the following markers: CD3, CD4, CD8, CD45RA, CCR7, CD27, CD28, CD38, HLA-DR, Ki-67, PD-1. Activated CD38+ HLA-DR+ CD8 T cells at the peak of activation/proliferation will be isolated by flow cytometric sorting followed by DNA and RNA isolation. RNA will be used to transcriptionally profile CD8 T cells responding to therapy using RNAseq. Furthermore, we will use DNA isolated from activated CD8 T cells in the peripheral blood and from frozen tumor tissue to analyze and compare the T cell receptor repertoire of activated/proliferating CD8 T cells in the blood and tumor-infiltrating lymphocytes in the obtained biopsy. It has recently been shown that a particular subset of PD-1+ CD8 T cells expressing the transcription factor TCF-1 possesses stem cell-like feature and is responsible for the proliferative burst of antigen-specific CD8 T cells following PD-1 pathway in a mouse model of persistent viral infection (39). Two recent studies also demonstrated that costimulatory signaling through CD28 is required for CD8 T cell proliferation following PD-1 pathway blockade (40, 41). We hypothesize that increased numbers of CD28+ and/or TCF-1+ among PD-1+ CD8 T cells will be predictive of response to PD-1 pathway blockade. To test this hypothesis, we will characterize tumor-infiltrating lymphocytes by immunofluorescent staining of FFPE sections using antibodies directed against CD4, CD8, PD-1, CD28, TCF-1 as well as additional markers, and correlate with the observed CD8 T cell responses in the blood as well as with clinical outcome.

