8. STATISTICAL METHODS

Power Caclulation: From the MIRI study, the 1-year PFS rate for class I and II combined was 43.8% (95% CI: 38.6 - 49.7%) Assuming a one sided alpha of 0.05 and an 85% power to detect an improvement in 1-yr PFS from 40% to 55% we estimate 46 patients will need to be accrued in 2.5 years and followed for an additional 2 years (estimated maximum total of 51 patients). Accounting for a 20% drop out rate, 62 patients will need to be consented. The sample size calculation was based on assumptions of exponentially distributed death times and use of the exponential MLE test (42). Definition of clinical outcomes: PFS is defined as months from treatment started to evidenced progression or death and censored at last follow up without progression, and OS is defined as months from treatment started to death or censored at last follow up if alive.

Analysis plan: For primary objective, the 1-yr PFS and its 95% confidence interval will be estimated by Kaplan-Meier method for all patients, as well as in each stratum defined by p16 and RPA status, but this study is not powered at the level of subgroups. For the secondary objectives, Kaplan-Meier method will be used to assess 1-yr OS, PFS, or pattern of failure, and the incidence rate of acute and late toxicities will be described as frequency and percentage. QOL will be summarized by mean and standard deviation. For exploratory objectives, the predictability of related biomarkers (baseline PDL1 status, T-cell activation biomarkers, CD28 and TCF1 positivity on T lymphocytes and other biomarkers) to clinical

outcomes (OS and PFS) will be explored using both univariate and multivariable Cox proportional hazards model controlling for potential confounders.

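### On-treatment T-cell activation has no stated timepoint, landmark or time-dependent term in the Cox models, so a summary over several draws would make a null marker look favourable

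*Combined protocol and SAP*

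**What the plan says.** Section 8 (Statistical Methods) lists the markers for the exploratory objective as baseline PD-L1 status, "T-cell activation biomarkers, CD28 and TCF1 positivity on T lymphocytes and other biomarkers". They are to be related to OS and PFS by univariate and multivariable Cox models with adjustment for confounders. Only PD-L1 is labelled baseline. The clock for PFS is explicit: "PFS is defined as months from treatment started to evidenced progression or death and censored at last follow up without progression". OS starts at the same point.

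Section 6.2 has blood drawn at baseline and "prior to each nivolumab infusion during radiation therapy; subsequently blood will be obtained at weeks 18, 30 52, and 104". In the Treatment Study Calendar, research blood is marked in the week-52 and week-104 columns, whose headings also allow the visit to fall at disease progression. A calendar footnote lets sites limit specimens to six draws per patient.

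Section 6.3 explains why activation is followed: in other PD-1 cohorts, a rise in activated CD8 T cells under treatment went with outcome. The word peak occurs there once, for a laboratory step: "Activated CD38+ HLA-DR+ CD8 T cells at the peak of activation/proliferation will be isolated by flow cytometric sorting". TCF-1 is to be stained on FFPE tumor sections. CD28 is on those sections and also in the blood panel.

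**The concern.** Activation in response to nivolumab can only be observed after treatment starts, whereas PFS and OS already run from that start. A patient with an event before week 18 contributes at most five scheduled draws (baseline and weeks 0, 2, 4 and 6). A patient event-free at two years contributes nine. The largest of nine values tends to exceed the largest of five even when the marker has nothing to do with outcome. Entered as a fixed covariate from treatment start, such a summary carries information about how long the patient stayed event-free. This is immortal-time bias.

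The bias has a direction. It favours high activation, which is the result section 6.3 leads one to expect. A positive finding on the only exploratory objective could then not be told apart from an artefact of the sampling schedule.

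**Working it through.** **1. The plan's own figure.** The documents give no sample size for the biomarker models, so the check starts from the primary design (1-year PFS 40% versus 55%, one-sided alpha 0.05, power 85%, 2.5 years' accrual, 2 years' further follow-up). Section 8 bases it on "assumptions of exponentially distributed death times and use of the exponential MLE test".

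- Hazard ratio = ln(0.55)/ln(0.40) = 0.652, so ln(HR) = −0.427.
- Events = (1.645 + 1.036)² / 0.427² = 39.4.
- Yearly hazard under the alternative = −ln(0.55) = 0.598. Event probability = 1 − (e^(−0.598×2) − e^(−0.598×4.5)) / (0.598×2.5) = 0.843.
- N = 39.4 / 0.843 = 46.8, against the stated 46 (power at 46 is 84.5%). The stated size is reproduced closely, so n=46 and these PFS rates are used below.

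**2. Does the number of draws depend on outcome?** Calendar weeks count from the start of radiation and the first nivolumab dose is at week −2. From first dose, the draws therefore fall at 0, 2, 4, 6, 8, 20, 32, 54 and 106 weeks. Weekly hazard = −ln(S)/52.

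| 1-year PFS | Event before week-6 draw (8 weeks) | Event-free at week-52 draw (54 weeks) |
|---|---|---|
| 40% | 1 − e^(−0.01762×8) = 13.1% | e^(−0.01762×54) = 39% |
| 55% | 1 − e^(−0.01150×8) = 8.8% | e^(−0.01150×54) = 54% |

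The later draws are strongly conditional on outcome. The radiation-phase draws are only mildly so.

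**3. Null simulation.** PFS is exponential, with 1-year PFS of 40% or 55% and censoring at 106 weeks. The marker is normal and unrelated to PFS. Except in the progression-draw row, blood stops at the event. The Cox test is two-sided at 5%, and HRs are medians per SD. The within-patient correlation between draws is an assumption, because the documents give none; 0.5 to 0.8 is used. With 1,500 trials per setting, the simulation standard error is about 0.6 percentage points at 5%, √(0.05×0.95/1500), and 1.0 at 20%.

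| Covariate | False positives | Median HR |
|---|---|---|
| Peak over all draws, from treatment start | 9–20% | 0.83–0.91 |
| Same, plus a draw at progression | 6–13% | below 1 |
| Peak over the first six draws only | 6–11% | below 1 |
| Maximum increase from baseline | 12–20% | below 1 |
| Peak over draws to week 6, no landmark | 5.7–7.2% | 0.93–0.97 |
| Baseline value | 4.8–5.4% | 0.99–1.00 |
| Draws to week 6, landmark at week 6 | about 5–6% | 0.99–1.00 |
| Running peak as time-dependent covariate | 5.1–5.6% | 0.99–1.00 |

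For the peak over all draws, correlation drives the size: 17–20% at 0.5 and 9–10% at 0.8. At the extreme of zero correlation it is 43–51% (HR 0.68–0.70). For maximum increase, a high correlation gives no relief, because subtracting the baseline removes the patient's shared level and leaves the draw-to-draw variation: at 0.8 it is still 16.3–18.9% (HR 0.83–0.85), or 13.1–16.8% with a progression draw.

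**4. A single fixed draw.** One value at a set visit, among patients event-free at that visit, gives about the nominal 5%, even with time counted from treatment start. Moving the origin does not change the Cox partial likelihood once everyone analysed has passed the visit. What matters is that the measurement window is the same for all and closes before the events being analysed.

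**The case against.** The strongest objection is that the covariate is undefined. A reader might infer that the plan enters the on-treatment peak into the Cox model. It does not say so: the one mention of a peak decides which cells are sorted for sequencing and receptor work. An analyst who took the baseline draw, or one fixed draw among patients still event-free, would have no bias. This stands, and the point is therefore conditional on the summary chosen. It does not dispose of the matter, because the stated rationale is a rise under treatment, the sampling is serial, and nothing in section 8 excludes a running summary.

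A reader might also infer that every listed marker except PD-L1 is affected. That is not supported. TCF-1 and tissue CD28 can come from the mandatory pre-treatment block and are then safe. Tissue at progression is optional, so the tissue timepoint is still worth naming.

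Two calendar provisions reduce the size. A draw at progression gives early progressors an extra chance of a high value. The simulation gives every PFS event such a draw, which is generous, since a death without progression would have none. The six-draw limit is optional and does not say which six are kept; the 6–11% assumes the first six.

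Finally, the analysis is exploratory, with no error rate or decision attached. This also stands, and it limits the importance of the point.

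**Conclusion.** The concern holds in conditional form. Section 8 allows an on-treatment summary over several draws to be analysed as if known at treatment start. If that is done, a null marker will tend to look protective for PFS. At n=46 and correlations of 0.5–0.8, the false-positive rate at a nominal 5% ranges from close to nominal (about 6%) to about 20%, depending on the summary, the draws used and whether blood is taken at progression. No single figure is defensible, because the correlation is assumed. The results also rest on exponential PFS and no missed draws.

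A reader might extend these figures to OS. The mechanism could apply there, but OS was not computed and no size is claimed. The primary 1-year PFS estimate does not use the biomarkers and is untouched. The label is a cheap improvement, confined to the exploratory objective.

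**What to change.** Add to section 8: any biomarker measured after treatment start will be analysed either with a landmark at the week-6 draw (draws up to that visit only, patients event-free at that time, time counted from the landmark) or as a time-dependent covariate. The ordinary Cox model from treatment start is kept for pre-treatment values. Naming the timepoint and summary for each marker belongs in the same place. In the time-dependent version, the value used at an event should come from draws before it, so a specimen taken at progression does not enter.

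The cost is one sentence and no change to data collection. The landmark analysis of PFS loses about 9–13% of patients, those with events before it: 0.088×46 ≈ 4 to 0.131×46 ≈ 6 of 46. That number should be reported. The time-dependent version excludes no one for an early event.

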9. ADMINISTRATION, HANDLING OF DATA AND SAFETY MONITORING

9.1. PROTOCOL AMENDMENTS

Any changes to the protocol will be made in the form of an amendment and must be approved by the coordinating site IRB before implementation. Any modifications made to the protocol or informed consent document according to local requirements or any other reason may also require approval from sponsoring agencies.

9.2. INFORMED CONSENT

An investigator will explain to each subject the nature of the study, its purpose, procedures involved, expected duration, potential risks and benefits. Each subject will be informed that participation in the study is voluntary and that she may withdraw from the study at any time, and that withdrawal of consent will not affect her subsequent medical treatment. This informed consent will be given by means of a standard written statement and will be submitted for IRB approval prior to use. No patient will enter the study before her informed consent has been obtained. In accordance with the Health Information Portability and Accountability Act (HIPAA), the written informed consent document (or a separate document to be given in conjunction with the consent document) will include a subject authorization to release medical information to the Principal Investigator and supporting agencies and/or allow these bodies, a regulatory authority, or Institutional Review Board access to subjects' medical information that includes all hospital records relevant to the study, including subjects' medical history.

9.3. ETHICS AND GOOD CLINICAL PRACTICE

This study must be carried out in compliance with the protocol and Good Clinical Practice, as described in:

1. ICH Harmonized Tripartite Guidelines for Good Clinical Practice 1996.
2. US 21 Code of Federal Regulations dealing with clinical studies (including parts 50 and 56 concerning informed consent and IRB regulations).
3. Declaration of Helsinki, concerning medical research in humans (Recommendations Guiding Physicians in Biomedical Research Involving Human Subjects, Helsinki 1964, amended Tokyo 1975, Venice 1983, Hong Kong 1989, Somerset West 1996).

The investigator agrees to adhere to the instructions and procedures described in it and thereby to adhere to the principles of Good Clinical Practice that it conforms to.

9.4. REGULATORY AUTHORITIES

Institutional Review Board

Information regarding study conduct and progress will be reported to the Institutional Review Board (IRB) per the current institutional standards of each participating center.

9.5. DATA QUALITY ASSURANCE

9.5.1 Data Management

All information will be collected on study-specific case report forms by the study staff at each institution. The necessary forms will be provided to each site by the Coordinating Center.

The completed forms will be forwarded to the Coordinating Center for central review and inclusion in the study dataset with relevant source documentation as outlined in the case report forms. The data submission schedule is as follows:

At the time of registration:

- Registration Form
- Informed Consent Form (signed by the subject)
- Eligibility Checklist
- Source documents related to eligibility.

Within 2 weeks after registration:

- Baseline study case report forms
- Pertinent source documents

Within 2 weeks after 30 day follow-up:

- On study case report forms
- Pertinent source documents

All study data will be reviewed for completeness and accuracy by the Protocol Chair. The Principal Investigator (or his/her designee) at each respective institution is responsible for review, and ensuring the completeness and accuracy, of the data generated by his/her institution. The study data will also be periodically reviewed by the Emory Winship Cancer Institute Clinical Research Office.

9.5.2. Meetings and Conference Calls

Scheduled meetings and conference calls will take place as needed with the PI and co-investigators and study personnel involved at coordinating center and participating site. In addition, separate meetings will be scheduled and include the protocol principal investigator, study coordinator(s), data manager(s). During these meetings matters related to the following will be discussed: safety of protocol participants, validity and integrity of the data, enrollment rate relative to expectation, characteristics of participants, retention of participants, adherence to protocol (potential or real protocol violations), data completeness, and progress of data for objectives.

9.5.3. Monitoring and Auditing

The Emory Winship Cancer Institute (Winship) clinical trials office will serve as the coordinating center for the Emory patients. The coordinating center will review responses and toxicity and report these to the regularly scheduled meetings of the DSMC of the Emory Winship Cancer Institute. Each participating site is expected to have its own data monitoring and safety plan (DMSP) with regard to forwarding information to their IRBs. If the data reveals a change in the risk/benefit ratio, the investigator will notify the IRB and the PI.

The PI and co-investigators will review the data and forward any changes or protocol amendments to the IRBs. All serious adverse events will be reported immediately to the IRB. All study participant information will be kept in a confidential manner by the assigning of a random number to each study participant. All data will be kept confidential as per institutional guidelines and policies. Any breach of confidentiality is a serious matter and conflicts with institutional policies and will be reported to the IRB. A cumulative summary of all adverse events occurring on this study and a report of the data safety and monitoring plan will be submitted to the IRBs with the annual renewal reports.

The Data and Safety Monitoring Committee (DSMC) of the Winship Cancer Institute will provide oversight for the conduct of this study. The DSMC functions independently within Winship Cancer Institute to conduct internal monitoring functions to ensure that research being conducted by Winship Cancer Institute Investigators produces high-quality scientific data in a manner consistent with good clinical practice (GCP) and appropriate regulations that govern clinical research. Depending on the risk level of the protocol, the DSMC review may occur every 6 months or annually. For studies deemed High Risk, initial study monitoring will occur within 6 months from the date of the first subject accrued, with 2 of the first 5 subjects being reviewed. For studies deemed Moderate Risk, initial study monitoring will occur within 1 year from the date of the first subject accrued, with 2 of the first 5 subjects being reviewed. Subsequent monitoring will occur in routine intervals per the Winship Data and Safety Monitoring Plan (DSMP).

The DSMC will review pertinent aspects of the study to assess subject safety, compliance with the protocol, data collection, and risk-benefit ratio. Specifically, the Winship Cancer Institute Internal Monitors assigned to the DSMC may verify informed consent, eligibility, data entry, accuracy and availability of source documents, AEs/SAEs, and essential regulatory documents. Following the monitoring review, monitors will provide a preliminary report of monitoring findings to the PI and other pertinent individuals involved in the conduct of the study. The PI is required to address and respond to all the deficiencies noted in the preliminary report. Prior to the completion of the final summary report, monitors will discuss the preliminary report responses with the PI and other team members (when appropriate). A final monitoring summary report will then be prepared by the monitor. Final DSMC review will include the final monitoring summary report with corresponding PI response, submitted CAPA (when applicable), PI Summary statement, and available aggregate toxicity and safety data.

The DSMC will render a recommendation and rating based on the overall trial conduct. The PI is responsible for ensuring that instances of egregious data insufficiencies are reported to the IRB. Continuing Review submissions will include the DSMC recommendation letter. Should any revisions be made to the protocol-specific monitoring plan after initial DSMC approval, the PI will be responsible for notifying the DSMC of such changes. The Committee reserves the right to conduct additional audits if necessary.

The trial be monitored at each other site by having sites participate in the Emory working group meetings occurring every Thursday morning at 745 AM (EST); the sites will be providing information and updates on their enrolled patients to the Emory HNCA working group; this will be a weekly meeting;

The following applies for monitoring of Sub-sites:

At the time of study initiation at a non-Emory site, the Emory Principal Investigator, Winship regulatory specialist, and Winship research coordinators will perform a site initiation teleconference. During this teleconference, the Emory team will review the study, enrollment, reporting, and regulatory compliance. The participating site will have internal monitoring meetings. These meetings which will include the participating site investigator, the clinical research coordinator and the regulatory affairs coordinator, will meet at least on a monthly basis to review and discuss study data to ensure subject safety. The research coordinators will maintain a spread sheet which will be de-identified and will summarize all the patient data for subjects actively being treated on the trial as well as a roadmap detailing pending tests/treatments for each individual subject. The spread sheet will be shared with the Emory PI via e-mail monthly. Teleconferences will be conducted weekly between the PI at Emory and the research team at the participating site(s). The purpose of the meetings is to discuss the enrollment, regulatory updates, monitor toxicities, and evaluate the progress of the trial. A record of the teleconferences will be kept in the regulatory binder. Scheduled teleconferences may stop after all patients have completed assigned protocol therapy and the PI at Emory will

communicate with participating sites via email as needed. This communication will also be maintained in the regulatory binder. Chart reviews will be performed on selected cases by the participating site staff to confirm that the data collection is accurate.

Winship's MSC will perform an on-site or remote monitoring visit within the first three months of enrollment of the first subject. Quarterly monitoring visits will occur (annually once onsite and three times remotely) until subject follow-up is terminated. Monthly reviews of data in OnCore will be conducted to ensure compliance or identify discrepancies.

